## 1.2 Product Background and Clinical Information

The active pharmaceutical ingredient of SPD489 is (2S)-2,6-diamino-N-[(1S)-1-methyl-2-phenylethyl] hexanamide dimethanesulfonate.

Figure 1 shows the chemical structure of the active pharmaceutical ingredient:

**Figure 1 Chemical Structure of the Active Pharmaceutical Ingredient**

Always refer to the latest version of the SPD489 IB for the most accurate and current information regarding the efficacy and safety of SPD489.

### 1.2.1 Preclinical Information

Lisdexamfetamine is a pharmacologically inactive prodrug. After ingestion, it is converted in the blood to *d*-amphetamine (responsible for pharmacological activity) and *l*-lysine (a naturally occurring essential amino acid). A comprehensive set of studies has been conducted to evaluate the pharmacological and toxicological properties associated with the parent compound lisdexamfetamine. The safety profiles associated with *d*-amphetamine and *l*-lysine are well established.

All safety and toxicology studies, except the single-dose acute toxicity study in rats, were conducted in compliance with Good Laboratory Practice.

Complete preclinical information is presented in the current SPD489 IB.

### 1.2.2 Clinical Information

The pharmacological profile of lisdexamfetamine and the pharmacologically active metabolite *d*-amphetamine have been well-characterized in studies enrolling children, healthy adults, and adults with a history of stimulant abuse. These studies have demonstrated that oral administration of SPD489 resulted in a predictable *d*-amphetamine pharmacokinetic profile with low intrasubject and intersubject variability. The *d*-amphetamine  $AUC_{0-\infty}$  and  $C_{max}$  generally behaved in a linear, dose-proportional manner. The weight-normalized *d*-amphetamine  $AUC_{0-\infty}$  is similar for children and adults, with  $t_{max}$  and  $t_{1/2}$  consistent across age groups.

In the ADHD Clinical Development Program, the efficacy of SPD489 for the treatment of ADHD has been demonstrated for children, adolescents, and adults with ADHD. Substantial evidence of efficacy was provided in well-controlled studies, where SPD489 was shown to be effective compared to placebo. SPD489 was associated with a statistically significant, clinically meaningful improvement in ADHD symptoms, functional outcomes, and health-related quality of life compared to placebo, in studies that used a variety of study designs, a variety of validated assessments, and a variety of raters.

The well-characterized SPD489 safety profile was consistent with that of other stimulants used in the treatment of ADHD. When the safety results from the 15 completed Phase 2-4 clinical studies in the ADHD Clinical Development Program were examined, the majority of TEAEs were mild or moderate in severity, and no differences due to age or sex were noted. The most frequently reported adverse events (AEs) were those typically associated with stimulant therapy (including decreased appetite, insomnia, headache, dry mouth, irritability, upper abdominal pain, and weight decrease), or potentially attributable to intercurrent illnesses (eg, upper respiratory tract infection and nasopharyngitis). These TEAEs were generally non-serious and were considered by the investigator to be resolved during study participation.

Stimulant medications like SPD489 cause a modest increase in average blood pressure (about 2-4 mmHg) and average pulse (about 3-6 bpm). Individuals may have larger increases.

Always refer to the latest version of the SPD489 IB for the overall risk/benefit assessment and the most accurate and current information regarding the drug metabolism, pharmacokinetics, efficacy, and safety of SPD489.

## 2 STUDY OBJECTIVES AND PURPOSE

### 2.1 Rationale for the Study

Based on IMS Health data and discussion at the Food and Drug Administration (FDA) Pediatric Advisory Committee in September 2012 ([Mistry and Chai 2012](#)), it has been noted that there is off-label use of SPD489 in children under 5 years old (4%, or approximately 100,000 patients between February 2007 and March 2012). The lack of controlled data regarding the safety and efficacy of SPD489 in the preschool ADHD population, in concert with the prevalence of off-label prescribing of SPD489 supports the need for SPD489 studies in the preschool ADHD population. Importantly, it is not known if the therapeutic effects of stimulant medications in school age children with ADHD can be extrapolated to preschool children with ADHD. There are some indications that the effect size may be reduced ([Greenhill et al. 2006](#)). There may also be differences in the safety and pharmacokinetic profiles ([Wigal et al. 2007](#); [Wigal et al. 2006](#)).

However, recent data from Shire SPD489-211 study preschool aged children with ADHD suggests the safety and tolerability profile of SHP489 is similar to that observed in trials with children 6 to 12 years old, adolescents and adults. The efficacy results of the SPD489-211 study, were also comparable to older subjects and revealed a mean decrease from baseline of -26.1 (95% CI: -32.2, -20.0) in the ADHD-RS-IV Preschool Version total score, suggesting a robust similar improvement in ADHD symptoms.

In summary given the abundance of information regarding the safety and efficacy of amphetamines; the very well-established PK profile of SPD489; the similar efficacy and safety findings between populations with ADHD covering the age span from 6 to 55 years; and the PK, safety, and efficacy data from Study SPD489-211 in preschoolers (aged 4-5 years) with ADHD, it is expected that findings from previous trials in older age groups can be extrapolated to preschool patients with ADHD.

### 2.2 Study Objectives

#### 2.2.1 Primary Objectives

To evaluate the efficacy of SPD489 compared to placebo in preschool children (4-5 years of age inclusive at the time of consent) with ADHD. The primary measure of efficacy will be the clinician-administered ADHD Rating Scale Preschool Version (ADHD-RS-IV Preschool Version) Total Score.

#### 2.2.2 Secondary Objectives

- **Key secondary:** To evaluate the efficacy of SPD489 compared to placebo, using the global clinical measure of improvement, the Clinical Global Impression-Global Improvement (CGI-I) Scale.

- **Secondary:**
  - To evaluate the dose response relationship in preschool children with ADHD, using the ADHD-RS Preschool Version Total Score.
  - To evaluate the safety and tolerability of SPD489 based on the occurrence of treatment-emergent adverse events (TEAEs), specific evaluation of vital signs (systolic and diastolic blood pressure and pulse), height, weight, and body mass index (BMI), clinical laboratory evaluations, and electrocardiogram (ECG) results, sleep assessment, and the Columbia Suicide Rating Scale (C-SSRS).

### 3 STUDY DESIGN

#### 3.1 Study Design and Flow Chart

Approximately 245 subjects will be screened to randomize approximately 195 subjects in a 5:5:5:5:6 ratio to SPD489 5, 10, 20, 30 mg dose strength or placebo to achieve 156 completers for this Phase 3 double-blind, placebo-controlled, fixed-dose study to evaluate the efficacy of SPD489 10, 20, and 30 mg pooled together compared to placebo, administered as a daily morning dose in the treatment of preschool children 4-5 years of age with ADHD.

Approximately 25% of the subjects enrolled will be female, consistent with the literature-defined gender distribution in ADHD clinic samples ([Szatmari et al. 1989](#); [Wallis et al. 2008](#); [Thapar 2002](#)).

A randomized fixed-dose design is used to avoid baseline characteristics selection bias for different treatment groups on the part of the participants and investigators. Blinded treatment is used to reduce potential bias during data collection and evaluation of clinical results. The placebo arm is used to control the subject's expectation that a treatment would have an effect, to optimize sensitivity, to maintain the scientific rigor of the study, and to validate the study internally.

[figure not shown]
The study will have 4 periods as outlined below and in [Figure 2](#):

- (1) Screening and Washout
- (2) Fixed-dose titration
- (3) Dose-maintenance
- (4) Safety Follow-up.

The duration of the double-blind evaluation period (Fixed-dose titration and Dose-maintenance Periods) will be 6 weeks.

SPD489 will be provided in dose strengths of 5, 10, 20, and 30 mg. Matching placebo will also be provided.

Figure 2 Study Design Flow Chart

ET=early termination; V=visit; W=week, WO=washout.

### 3.2 Duration and Study Completion Definition

The subject's maximum duration of participation is expected to be approximately 11 weeks. The study will be completed in approximately 24 months.

The Study Completion Date is defined as the date the final subject, across all sites, completes their final protocol-defined assessment. Please note that this includes the follow-up visit or contact, whichever is later. The Study Completion Date is used to ascertain timing for study results posting and reporting.

### 3.3 Sites and Regions

This study will be conducted in up to 60 sites in North America.

## 4 STUDY POPULATION

Each subject must participate in the informed consent process and provide written informed consent and/or assent, as per IRB/EC requirements, before any procedures specified in the protocol are performed.

### 4.1 Inclusion Criteria

The subject will not be considered eligible for the study without meeting all of the criteria below (including test results).

1. Subject is a male or female aged 4-5 years inclusive at the time of consent.
2. Subject's parent(s) or legally authorized representative (LAR) must provide signature of informed consent, and there must be documentation of assent (if applicable) by the subject in accordance with the International Council on Harmonisation (ICH) Good Clinical Practice (GCP) Guideline E6 (1996), any updates or revisions, and applicable regulations, before completing any study related procedures.
3. Subject and parent(s)/LAR are willing and able to comply with all of the testing and requirements defined in the protocol, including oversight of morning dosing. Specifically, the parent(s)/LAR must be available at approximately 7:00AM ( $\pm 2$  hours) to dispense the dose of investigational product for the duration of the study.
4. Subject must meet DSM-IV-TR criteria for a primary diagnosis of ADHD (any sub-type) based on a detailed psychiatric evaluation.
5. Subject has an ADHD-RS-IV Preschool Version Total Score at the baseline visit (Visit 0) of  $\geq 28$  for boys and  $\geq 24$  for girls.
6. Subject has a Clinical Global Impressions – Severity of Illness (CGI-S) score  $\geq 4$  at the baseline visit (Visit 0).
7. Subject has a Peabody Picture Vocabulary Test standard score of  $\geq 70$  at the screening visit (Visit -1).
8. Subject has undergone an adequate course of non-pharmacological treatment OR the subject has a severe enough condition to consider enrollment without undergoing prior non-pharmacological treatment, based on investigator judgment.
9. Subject has, in the opinion of the investigator, participated in a structured group activity (eg, preschool, sports, Sunday school) so as to assess symptoms and impairment in a setting outside the home.
10. Subject has lived with the same parent(s) or guardian for  $\geq 6$  months.

#### **4.2 Exclusion Criteria**

Subjects are excluded from the study if any of the following exclusion criteria are met.

1. Subject is required to or anticipates the need to take any prohibited medications or medications that have CNS effects or have an effect on performance, such as sedating antihistamines and decongestant sympathomimetics, or other monoamine oxidase inhibitors. Stable use of bronchodilator inhalers is not exclusionary.
2. Subject has taken another investigational product or has taken part in a clinical study within 30 days prior to the screening visit (Visit -1).
3. Subject is well-controlled on his/her current ADHD medication with acceptable tolerability.
4. Subject has a concurrent chronic or acute illness (such as severe allergic rhinitis or an infectious process requiring antibiotics), disability, or other condition that might confound the results of safety assessments conducted in the study or that might increase risk to the subject.

Similarly, the subject will be excluded if he or she has any additional condition(s) that, in the investigator's opinion, would prohibit the subject from completing the study or would not be in the best interest of the subject. The additional conditions would include any significant illness or unstable medical condition that could lead to difficulty complying with the protocol. Mild, stable asthma is not exclusionary.

5. Subject has glaucoma.
6. Subject has failed to fully respond, based on investigator judgment, to an adequate course of amphetamine therapy.
7. Subject has a documented allergy, hypersensitivity, or intolerance to amphetamine or to any excipients in the investigational product.
8. Subject has a known family history of sudden cardiac death or ventricular arrhythmia.
9. Subject has a blood pressure measurement  $\geq 95$ th percentile for age, sex, and height at the screening visit (Visit -1) or the baseline visit (Visit 0) or a history of moderate or severe hypertension.
10. Subject has a known history of
  - symptomatic cardiovascular disease
  - unexplained syncope
  - exertional chest pain
  - advanced arteriosclerosis
  - structural cardiac abnormality
  - cardiomyopathy
  - serious heart rhythm abnormalities
  - coronary artery disease
  - other serious cardiac problems placing them at increased vulnerability to the sympathomimetic effects of a stimulant drug.
11. Subject has any clinically significant clinical laboratory abnormalities at the screening visit (Visit -1) or ECG at screening visit (Visit -1) or baseline visit (Visit 0) based on investigator judgment.
12. Subject has a history of hyperthyroidism, or current abnormal thyroid function, defined as abnormal thyroid stimulating hormone (TSH) and thyroxine (T4) at the screening visit (Visit -1). Treatment with a stable dose of thyroid medication for at least 3 months is permitted.
13. Subject has a current, controlled (requiring medication or therapy) or uncontrolled, co-morbid psychiatric disorder including but not limited to any of the below co-morbid Axis I disorders and Axis II disorders:
  - i. post-traumatic stress disorder or adjustment disorder

- ii. bipolar illness, psychosis, or a family history of these disorders
  - iii. pervasive developmental disorder
  - iv. obsessive-compulsive disorder (OCD)
  - v. psychosis/schizophrenia
  - vi. a serious tic disorder, or a family history of Tourette's disorder
  - vii. Subject is currently considered a suicide risk in the opinion of the investigator, has previously made a suicide attempt, or has a prior history of, or is currently demonstrating active suicidal ideation.
  - viii. a history of physical, sexual, or emotional abuse
  - ix. any other disorder or agitated state that in the opinion of the investigator, contraindicates SPD489 or lisdexamfetamine dimesylate treatment or confound efficacy or safety assessments.
14. Subject has initiated behavioral therapy within 1 month of the baseline visit (Visit 0). Subject may not initiate behavioral therapy during the study.
15. Subject has a height  $\leq$ 5th percentile for age and sex at the screening visit (Visit -1).
16. Subject has a weight  $\leq$ 5th percentile for age and sex at the screening visit (Visit -1).
17. Subject lives with anyone who currently abuses stimulants or cocaine.
18. Subject has a history of seizures (other than infantile febrile seizures).
19. Subject is taking any medication that is excluded per the protocol.

### **4.3 Reproductive Potential**

#### **4.3.1 Female Contraception**

No female subjects in this study are of child bearing potential. All female subjects in this study are pre-menarchal, less than age 9 years, and Tanner Stage 1.

### **4.4 Discontinuation of Subjects**

A subject (parent[s]/LAR) may withdraw from the study at any time for any reason without prejudice to their future medical care by the physician or at the institution. The investigator or sponsor may withdraw the subject at any time for any reason (eg, in the interest of subject safety). The investigator is encouraged to discuss withdrawal of a subject from the clinical study with the medical monitor.

Upon discontinuation of the investigational product, regardless of the reason, the evaluations listed for Visit 6 are to be performed as completely as possible. Whenever possible, all discontinued subjects should also undergo the protocol-specified follow-up. Comments (spontaneous or elicited) or complaints made by the subject must be recorded in the source documents. The reason for termination and date of stopping investigational product must be recorded in the case report form (CRF) and source documents.

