**Table 1 Schedule of Assessments**

Period	Screening and Washout			Dose-titration			Dose-maintenance			Safety Follow-up
	-1 (Screening)	Washout Telephone Call	0 (Baseline)	1	2	3	4	5	6/ ET	Telephone Call
Assessment Week	-4 to -1	-1	0	1	2	3	4	5	6	7
Assessment Day	-28 to -1		0	7	14	21	28	35	42	49
CGI-I k				✓	✓	✓	✓	✓	✓	
CSHQ k			✓	✓	✓	✓	✓	✓	✓	
Sleep diary l			✓	✓	✓	✓	✓	✓	✓	
C-SSRS k	✓		✓	✓	✓	✓	✓	✓	✓	
Suitability of subject to remain in study m			✓	✓	✓	✓	✓	✓		
Access IWRS	✓		✓	✓	✓	✓	✓	✓	✓	
Investigational product distributed			✓	✓	✓	✓	✓	✓		
Investigational product returned				✓	✓	✓	✓	✓	✓	
Investigational product compliance				✓	✓	✓	✓	✓	✓	
Concomitant medications	✓	✓	✓	✓	✓	✓	✓	✓	✓	✓
Adverse events	✓	✓	✓	✓	✓	✓	✓	✓	✓	✓

ADHD-RS-IV=ADHD Rating Scale-IV; BMI=body mass index; CGI-I=Clinical Global Impressions-Global Improvement; CGI-S=Clinical Global Impressions-Severity of Illness; CSHQ=Children's Sleep Habits Questionnaire; C-SSRS=Columbia-Suicide Severity Rating Scale; ECG=Electrocardiogram; ET=early termination; IWRS= Interactive Web Response System; K-SADS-PL=Kiddie-Schedule for Affective Disorders and Schizophrenia for School-age Children-Present and Lifetime Version-Diagnostic Interview

a Visit windows are ±3 days [in reference to the baseline visit (Visit 0) date] during the Fixed-dose titration and Dose-maintenance Periods. Safety Follow-up Telephone Call window is +3 days.

b Inclusion/exclusion criteria must be reviewed at the Washout Telephone Call and at the baseline visit (Visit 0).

c Medication history will include a lifetime history of pharmacologic and non-pharmacologic therapies for ADHD.

d An abbreviated physical examination, 12-lead ECG, and all clinical laboratory tests must be repeated and results reviewed by the investigator prior to the baseline visit (Visit 0) if more than 30 days have elapsed since the safety measurements at the screening visit (Visit -1) were collected. Results must be obtained and reviewed prior to determining eligibility.

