### 7.1.2.3 End-of-Study Visit (Visit 6/Early Termination)

All randomized subjects who complete the study or discontinue early will complete Visit 6/early termination (ET).

[Table 1](#) lists the procedures to be completed at Visit 6/ET and should serve as the primary point of reference regarding visit-specific study procedures.

Further clarification on the procedures performed during Visit 6/ET is provided below:

- Unused investigational product and empty containers will be collected to calculate medication compliance.
- After 5 minutes rest, blood pressure and pulse will be collected 3 times (with at least 2 minutes in between each collection) during the visit. The average of each set of 3 measurements will be used to determine continued participation in the study (see [Section 4.4.1](#)).

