### 7.1.3 Safety Follow-up Period

The follow-up period for this protocol is 7 days +3 days from the last dose of investigational product.

At the end of this period there will be a telephone call initiated by the site staff to query for serious adverse events (SAEs), AEs, and concomitant treatments. All AEs and SAEs that are not resolved at the time of this contact will be followed to closure (see [Section 8.1](#)).

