## 7.2 Study Evaluations and Procedures

The individual indicated in each scale description will perform all assessments listed below. Assessments are to be performed according to the schedule shown in [Table 1](#). Care must be taken by the site personnel or the investigator to fully explain the scale prior to completion.

If the subject terminates treatment early, all assessments listed in [Table 1](#) for Visit 6/ET and the Safety Follow-up Call should be completed. Whenever possible, raters (including parent(s)/LAR and the investigator or site designee) observing the subject's behavior should be consistent from visit to visit throughout the study.

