4.4 Full Analysis Set

The Full Analysis Set (FAS) will consist of all subjects in the Safety Analysis Set who have at least 1 post-dose ADHD-RS-IV-Preschool Version Total Score assessment.

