10. EFFICACY ANALYSES

The primary and key secondary analyses, including their sensitivity analyses, will be based on the FAS and will be conducted on either the interim analysis dataset, which is defined in Section 2.6, or all cumulative data up to study completion, whenever it is appropriate. Specifically, these analyses will compare placebo and pooled SPD489 10, 20, 30 mg dose strengths together, excluding the 5 mg arm. For primary and key secondary endpoints, statistical tests are planned to control the study-wise type I error at the 2-sided 5% level, as described in Section 2.6. All other statistical tests will be 2-sided hypothesis tests performed at the 5% level of significance, with no adjustment for multiplicity. All confidence intervals (CIs) will be 2-sided 95% CIs, unless stated otherwise. Additionally, the dose response relationship evaluations will be performed over the DRAS and using appropriate datasets. For this analysis, all randomized investigational product groups, which include 0 (placebo), 5, 10, 20, 30 mg (SPD489) dose strengths will be used.

Baseline for all efficacy analyses is defined as the last valid value for the efficacy assessment prior to the first dose of investigational product. An efficacy measurement that is assessed more than 3 days after the date of the last dose of investigational product will not be included for analysis.

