10.2 Sensitivity Analyses for the Primary Efficacy – Missing Not at Random

The primary efficacy analysis (MMRM) relies on the assumption that the missing data mechanism follows the missing at random (MAR) scenario. In this case, it is assumed that the reason for data being missing may depend on observed data, but not on the unobserved missing data. The likelihood-based MMRM analysis is an appropriate method for the statistical analysis under MAR assumption.

The following 2 sensitivity analysis models, which are within the pattern-mixture model framework, will be used to examine the robustness of the primary efficacy analysis results for the missing not at random (MNAR) mechanisms. Under MNAR, it is assumed that the reason for data being missing is related to the unobserved missing data.

Model 1: Placebo Multiple Imputation

Rationale: The imputations are based on the distribution of placebo group responses over time. The underlying assumption is that the missing data for a subject on the active treatment follow the distribution of the placebo responses, i.e., the mean values and intra-subject correlations based on the placebo responses will be applied.

The model is implemented in 3 steps: 1) imputations, 2) analysis of complete data sets, and 3) inference. Sample SAS codes are provided in [Appendix 2](#).

Step 1: Imputations

A total of 200 sets of posterior mean and co-variance estimates are extracted from the SAS MI procedure using the available non-missing placebo data. One hundred of the posterior sets will be applied to the pooled active treatment group, while the other 100 will be applied to the placebo group. One set of imputations for all missing values will be generated based on each variation of posterior estimates. All 100 datasets for imputations within a treatment group will be ordered from 1 to 100 and combined between pooled active treatment group and placebo, for a total of 100 completely imputed datasets.

Step 2: Analysis of Complete Datasets

The primary efficacy endpoint will be analyzed for each of the 100 complete datasets with imputed data using an analysis of covariance with treatment group as factors and the baseline value as a covariate.

Step 3: Inference

The LS mean difference estimates will be averaged, and the associated SEs will be summarized based on within-imputation and between-imputation variance using the SAS MIANALYZE procedure to yield a final estimate with associated 95% CI and p-value.

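### The early-termination rating has no deadline counted from the last dose, yet the SAP excludes any efficacy rating taken more than 3 days after it

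*Protocol*

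**What the plan says.** **Collection.** Protocol 4.4: "Upon discontinuation of the investigational product, regardless of the reason, the evaluations listed for Visit 6 are to be performed as completely as possible". Protocol 7.2 repeats the duty: "If the subject terminates treatment early, all assessments listed in" Table 1 for Visit 6/ET are to be completed. Protocol 7.1.2.3 applies the ET visit to every randomized child who stops early. Table 1 ticks both the ADHD-RS-IV and the CGI-I at Visit 6/ET.

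**Timing.** None of these sections gives a number of days from last dose to the ET visit. The on-study window in Table 1, footnote a, is counted from baseline: "Visit windows are ±3 days [in reference to the baseline visit (Visit 0) date] during the Fixed-dose titration and Dose-maintenance Periods". Protocol 7.1 says the same. The only contact timed from last dose is the safety telephone call (Protocol 7.1.3: "The follow-up period for this protocol is 7 days +3 days from the last dose of investigational product"), and it carries no efficacy rating.

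**Analysis.** SAP 10: "An efficacy measurement that is assessed more than 3 days after the date of the last dose of investigational product will not be included". The protocol applies a 3-day limit after last dose only to treatment-emergent adverse events (Protocol 9.9), not to efficacy. SAP 17 lists no changes from the protocol.

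**Missing data.** SAP 10.2: "The primary efficacy analysis (MMRM) relies on the assumption that the missing data mechanism follows the missing at random (MAR) scenario". SAP 10.1 adds that missing data are not imputed in the primary model.

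**The concern.** The two documents use different clocks. A site that follows the protocol has no reason to know that an ET rating on day 4 or later after the last capsule will not be analysed, and a late rating cannot be made timely afterwards.

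The rating at risk is usually the last one before the child leaves. Under missing at random, the model allows for dropout through the scores it can see. If a child stops because the current score is poor and that score is in the model, the stopping is explained by observed data. If the score has been excluded, stopping depends on a value the model does not have. Should that happen in different ways in the two arms, the Week 6 difference can shift. The same rule applies to the CGI-I, the key secondary endpoint.

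**Working it through.** **1. The plan's own figures (Protocol 9.6, SAP 2.5).** Inputs: 36 placebo and 90 pooled completers, difference 8.4, SD 14, two-sided 0.05, 20% dropout.

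- SE = 14 × √(1/36 + 1/90) = 2.76; 8.4/2.76 = 3.04; power = Φ(3.04 − 1.96) ≈ 0.86. With the two-look boundaries 0.0074 and 0.0477 at 60% information, power is 0.858.
- 156/0.80 = 195 randomized.

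Both stated figures (85% and 195) are reproduced. They rest on completers, so the point made here does not change them.

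**2. Early stoppers in the primary comparison.** The 5 mg arm is outside the primary and key secondary analyses. The other arms hold 21 of every 26 children: 195 × 21/26 = 157.5 randomized. Subtracting 126 completers leaves 31.5 early stoppers (22.5 pooled active, 9 placebo).

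**3. Ratings lost, by assumed late share** (the share is not in the documents):

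| ET ratings taken more than 3 days after last dose | Ratings excluded | Share of 157.5 |
|---|---|---|
| 10% | 3.15, about 3 | 2% |
| 25% | 7.9, about 8 | 5% |
| 50% | 15.75, about 16 | 10% |

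**4. An upper scenario.** Assume every child stops on a random day between weekly visits and every site waits for the next one. With the last dose k days after a visit, the gap is 7 − k days, which exceeds 3 when k is 3 or less.

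- k runs from 0 to 6: 4 of 7 days are late, and 4/7 × 31.5 = 18.
- k runs from 1 to 7 (a last dose on the morning of the next visit is possible): 3 of 7 days are late, and 3/7 × 31.5 = 13.5.

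So about 13 to 18 ratings.

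**5. Effect on the estimate.** This was simulated under assumptions that are not in the documents: 45 placebo and 112 active children, true difference −8.4, serial correlation 0.8, placebo stopping driven by the current score, active stopping random, and the ET score used at the time it was taken. With dropout of 17% on placebo and 20% on active:

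| ET scores lost | Estimate | Shift from no loss |
|---|---|---|
| none | −8.47 | – |
| 10% | −8.39 | 0.08 |
| 29% | −8.24 | 0.23 |
| 57% | −8.01 | 0.46 |

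The empirical standard error was about 2.67, so these shifts are 0.03 to 0.17 standard errors. A separate simulation with about 20% dropout per arm gave −8.41 with no loss, −8.19 at 29% and −7.98 at 57%. With the same score-driven stopping rule in both arms there was no shift (−8.40 against −8.42).

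**The case against.** The wording of Protocol 4.4 implies a prompt ET visit, not a wait for the next weekly one. Many stops would be decided at a visit: suitability is reviewed at each visit from 0 to 5 (Protocol 7.2.4.10), blood pressure is judged over consecutive visits (4.4.1.1), and a high pulse leads to an unscheduled visit within 1 business day (4.4.1.2). Unscheduled visits are allowed throughout (7.1.2.1, 7.1.2.2). Some stoppers are lost to follow-up and have no ET rating to exclude. The cut-off itself is defensible: a score more than 3 days after the last dose of a once-daily drug describes a child off treatment, and the adverse-event window uses the same limit. Earlier weekly scores stay in the model, and SAP 10.2 pre-specifies two analyses for data missing not at random.

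Most of this stands, and it lowers the likely number of late ratings. It does not remove the mismatch. Promptness is implied but no day limit is set. A cut-off suited to an on-treatment question is a reason to collect the rating inside it. The two SAP 10.2 models impute unobserved values; neither puts an excluded observed score back.

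Four stronger readings are tempting and not supported:

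- *The excluded ratings show why children stopped.* They show symptom state near stopping. The reason and stop date go on the CRF (Protocol 4.4, 4.4.2) and are kept.
- *More than half of all 39 planned dropouts lose their rating (4/7 × 39, about 22).* The 39 include the 5 mg arm, and the count needs every site to wait for the next weekly visit.
- *The primary result will be materially biased.* The simulated shift is small, toward the null, and absent if stopping works alike in both arms. Larger shifts (to −7.66 or −7.42) appeared only with placebo dropout of 37% to 38%, nearly twice the plan.
- *The FAS definition distorts the estimate.* SAP 4.4 asks for "at least 1 post-dose ADHD-RS-IV-Preschool Version Total Score assessment" and states no 3-day limit, so a child whose only score is a late one may be counted. That child adds no data to the MMRM; only a table count could differ.

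**Conclusion.** The mismatch is real: a rating that the protocol requires, taken when the protocol allows, can be excluded by the SAP. It is a data-quality weakness worth correcting, not a threat to the trial's conclusion. The likely loss cannot be read from the documents. About 3 to 16 ratings follow from assumed late shares of 10% to 50% among 31.5 early stoppers, and 13 to 18 is the upper scenario. At planned dropout the effect on the Week 6 difference is roughly 0.1 to 0.5 points toward the null. That size rests wholly on the assumed stopping mechanism and correlation, and it needs stopping to depend on the current score differently by arm. Sample size and power are unaffected.

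**What to change.** **Protocol 4.4, 7.1.2.3 and Table 1 footnote a:** require the ET ADHD-RS-IV and CGI-I to be rated within 3 days of the last dose whenever possible, matching SAP 10, and have the last-dose date confirmed at the rating. Later ET visits are still done for safety.

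**SAP 10 and 10.2:** report the number of ET ratings excluded by the 3-day rule, by arm and reason for stopping, and add a sensitivity analysis that includes them. This covers the ratings that remain late.

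**SAP 4.4 (minor clarification):** state whether a score outside the 3-day limit qualifies a child for the FAS.

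**Cost:** some ET visits must be arranged earlier than the next weekly visit, plus one extra table and one extra analysis. No assessments are added.
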